### **FEASIBILITY:**

A total of 1145 inpatient colonoscopies were done at Cleveland Clinic from April 2018 to April 2019, averaging 190 colonoscopies per month. Assuming a recruitment rate of 75 %, 12 months of recruitment will be needed to obtain a sample size of 1000 patients (250 per group) and complete our study.

### **BOWEL PREPARATION AGENTS:**

#### **CLENPIQ (SP/MC):**

##### **INDICATIONS/CONTRAINDICATIONS:**

The use of CLENPIQ will be studied in our project and compared to the standard of care which is golytely (4 L PEG-ELS). CLENPIQ is a combination of sodium picosulfate, a stimulant laxative, and magnesium oxide and anhydrous citric acid (SP/MC) which form magnesium citrate, an osmotic laxative, indicated for cleansing of the colon as a preparation for colonoscopy in adults. Contraindications to CLENPIQ use include 1) patients with severely reduced renal function (creatinine clearance less than 30 mL/minute) which may result in accumulation of magnesium, 2) gastrointestinal obstruction or ileus, 3) bowel perforation, 4) toxic colitis or toxic megacolon, 5) gastric retention, and 6) an allergy to any of the ingredients in CLENPIQ.

##### **ADVERSE EFFECTS:**

The safety and efficacy of CLENPIQ has been established based on adequate and well-controlled studies of another formulation of sodium picosulfate, magnesium oxide and anhydrous citric acid.

### **DRUG INTERACTIONS:**

Use caution when prescribing CLENPIQ for patients with conditions or who are taking medications that increase the risk for fluid and electrolyte disturbances or may increase the risk of renal impairment, seizure, arrhythmias, and prolonged QT in the setting of fluid and electrolyte abnormalities. This includes patients receiving drugs which may be associated with hypokalemia (such as diuretics or corticosteroids, or drugs where hypokalemia is a particular risk, such as cardiac glycosides) or hyponatremia. Use of caution is also advised when CLENPIQ is used in patients with severe active colitis, on nonsteroidal anti-inflammatory drugs (NSAIDS) or drugs known to induce Antidiuretic Hormone Secretion (SIADH), such as tricyclic antidepressants, selective serotonin re-uptake inhibitors, antipsychotic drugs and carbamazepine, as these drugs may increase the risk of water retention and/or electrolyte imbalance.

It is important to note that oral medications administered within one hour of the start of administration of CLENPIQ solution may be flushed from the GI tract and the medication may not be absorbed. Tetracycline and fluoroquinolone antibiotics, iron, digoxin, chlorpromazine, and penicillamine, should be taken at least 2 hours before and not less than 6 hours after administration of CLENPIQ to avoid chelation with magnesium. Prior or concomitant use of antibiotics with CLENPIQ may reduce the efficacy of CLENPIQ as conversion of sodium picosulfate to its active metabolite BHPM is mediated by colonic bacteria.

### **GOLYTELY (4-LITER PEG-ELS):**

#### **INDICATIONS/CONTRAINDICATIONS:**

GOLYTELY is indicated for bowel cleansing prior to colonoscopy and barium enema X-ray examination in adults. It is contraindicated in patients with gastrointestinal (GI) obstruction, ileus, or gastric retention, bowel perforation, toxic colitis or toxic megacolon or known allergy or hypersensitivity to any component of golytely.

#### **ADVERSE EFFECTS:**

Nausea, abdominal fullness and bloating are the most common adverse reactions (occurred in up to 50% of patients) to the administration of golytely. Abdominal cramps, vomiting and anal irritation occurs less frequently. These adverse reactions are transient and usually subside rapidly. Cases of urticaria, rhinorrhea, dermatitis and (rarely) anaphylactic reaction have been reported which may represent allergic reactions.

Published literature also contains isolated reports of serious adverse reactions following the administration of PEG-electrolyte solution products in patients over 60 years of age which include upper GI bleeding from Mallory-Weiss Tear, esophageal perforation, asystole, sudden dyspnea with pulmonary edema, and “butterfly-like” infiltrates on chest X-ray after vomiting and aspirating PEG.

#### **DRUG INTERACTIONS:**

Use of caution is advised when prescribing golytely for patients who are using medications that increase the risk for fluid and electrolyte disturbances or may increase the risk of seizures, arrhythmias, and prolonged QT in the setting of fluid and electrolyte abnormalities. Oral medication administered within one hour of the start of administration of golytely may be flushed from the gastrointestinal tract and the medication may not be absorbed properly. Concurrent use of stimulant laxatives like bisacodyl or sodium picosulfate with golytely may increase the risk of mucosal ulceration or ischemic colitis and will be avoided.

#### **STATISTICAL ANALYSIS:**

Descriptive data will be presented for all 4 groups; these include means  $\pm$  standard deviations, median [25th, 75th percentiles] or frequency (percent). Regression analysis will be used to assess the primary and secondary outcomes of interest; logistic regression will be used to model satisfactory bowel preparation and need of repeat procedure while proportional odds logistic regression will be used to model tolerability. For each model, the outcome of interest will be modeled as the dependent variable with the type of bowel preparation (PEG-ELS vs. SP/MC) and type of dose (single vs. split) as the independent variables; the interaction between these two will be tested and included in the models if  $p < 0.10$ . SAS (version 9.4, The SAS Institute, Cary, NC) will be used for all analyses and a  $p < 0.05$  will be considered statistically significant.

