### **METHODOLOGY:**

#### **STUDY DESIGN:**

A randomized, single-center, assessor-blinded trial will be conducted at Cleveland Clinic, a tertiary healthcare center in Ohio, United States. Eligible inpatients at the Cleveland Clinic scheduled for colonoscopy under conscious sedation or general anesthesia will be invited to participate.

Patients eligible for conscious sedation will be randomized at a 1:1:1:1 ratio to receive 1 of the 4 proposed bowel preparation regimens using block randomization. This will be done with a computer-aided system prior to study commencement. The four groups are as follows:

- Group A: 4 Liter PEG-ELS administered as a single day before dose the evening before the colonoscopy,
- Group B: 4 Liter PEG-ELS administered as a split dose the evening before and 4 hours prior to the colonoscopy (currently the standard to which other bowel regimens are compared),
- Group C: SP/MC administered as a single day before dose the afternoon or early evening before the colonoscopy,
- Group D: SP/MC administered as a split dose the afternoon or early evening day before and 4 hours prior to the colonoscopy.

Patients who require general anesthesia will be randomized at a 1:1 ratio to the single, ‘day before dose’ only groups for both PEG-ELS and SP/MC since the anesthesia protocol at our institution mandates strict enforcement of nothing per oral after midnight on the day of the procedure.

- Group E: 4 Liter PEG-ELS administered as a single day before dose the afternoon or early evening before the colonoscopy,
- Group F: SP/MC administered as a single day before dose the afternoon or early evening before the colonoscopy,

- All procedures will be done at the endoscopy suite on the main campus at Cleveland Clinic by a board certified gastroenterologist. The physician and the patients will not be blinded due to major differences in the volume and timing of the bowel cleansing regimens. Primary end-points of this study will be measured between the participants in the all 6groups.

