#### **PATIENT EDUCATION:**

There is an educational initiative currently underway at Cleveland Clinic to improve the inpatient colonoscopy experience which will also be applicable to all the patients enrolled in our study. The initiative entails:

- 1) Educating the nurses (via educational posters and small didactic sessions),

2) Educating the internal medicine and surgery residents who order the bulk of the inpatient colonoscopies (via educational posters and small didactic sessions),

3) Educating the patients (via detailed instructional pamphlets which will be distributed on the day before the colonoscopy)

Every patient who consents for inclusion in our study will also receive written instructions educating them about the appropriate preparation that needs to be undertaken to make their colonoscopy successful, with special emphasis on proper technique of the bowel cleansing process. Additionally, an investigator or study coordinator would be available to answer any questions that the patient might have related to the bowel purgatory process or the procedure itself.

A clear liquid diet is preferred after awakening the entire day before the procedure. Patients will not be excluded from participating in the study if they have eaten solid food the day before the procedure. Patients will be instructed to consume clear liquids (no solid food) once they begun consuming the bowel preparation until after their colonoscopy. To ensure better comprehension of the patient and success of the bowel cleansing process, the written instructions will specify drinks that qualify as clear liquids. The patient's in each group will be instructed to consume the bowel preparation agent as per their approved FDA labels. Administration of bowel preparations as a split dose is currently the recommendation of choice, for colonic cleansing prior to colonoscopy, in national guidelines (including American Society of Gastrointestinal Endoscopy, American College of Gastroenterology and United States Multi-Society Task Force for colorectal cancer screening).

1) 4 LITER PEG-ELS GROUP (CONSCIOUS SEDATION/SINGLE DOSE DAY BEFORE):

Group A will be instructed to drink the 4-liter PEG-ELS at rates of 8 ounces (240 ml) every 10 min the evening before their colonoscopy and finish drinking the bowel preparation in three hours. They may continue to drink additional clear liquids until 2 hours before their colonoscopy.

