Group E will be instructed to drink the 4-liter PEG-ELS at rates of 8 ounces (240 ml) every 10 min the afternoon or evening before their colonoscopy and finish drinking the bowel preparation within 3 hours and no later than midnight . They may continue to drink additional clear liquids until midnight and then nothing to eat or drink until after their colonoscopy.

6) SP/MC GROUP (GENERAL ANESTHESIA/SINGLE DOSE DAY BEFORE):

Group F will be instructed to drink sodium picosulfate, magnesium oxide and anhydrous citric acid (CLENPIQ) which is ready to drink and does not need to be diluted. Patients will consume the first bottle of SP/MC **the afternoon or evening** before their colonoscopy followed by at least five (5) 8-

ounce glasses of clear liquid consumed at their own pace, within the next 5 hours. The patient will consume the second bottle of SP/MC 5 hours after beginning the first bottle followed by at least 3 glasses of 8-ounce clear liquids which must be completed by midnight the day before the procedure. They may continue to drink additional clear liquids until midnight and then nothing to eat or drink until after their colonoscopy.

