### **SAMPLE SIZE CALCULATION:**

Preliminary data has been gathered over the last one year at Cleveland Clinic which has shown adequate bowel preparation rates (as defined by the reported preparation quality of good or excellent on the Aronchik scale) in about 46 % of all hospitalized patients undergoing colonoscopy. Due to the educational initiative currently underway at our institution, we will assume that the rates of adequate bowel preparation will be 50 % (which will be taken as the rate of adequate preparation in our control arm of the 4 L PEG-ELS). To demonstrate a 10 % increase in rates of adequate cleansing with the use of P/MC at a confidence level of 95% and a power of 85 %, a sample size of at least 886 subjects would be required. Counteracting for a possible difference that may exist between our estimated and existing rates of satisfactory bowel preparation, we will increase the sample size by at least 10 % for a total of 1000 patients (250 patients per group).

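### The plan does not say which groups enter the split-versus-single model; if general-anesthesia groups E and F do, the dose effect is partly confounded with sedation stratum

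*Combined protocol and SAP*

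**What the plan says.** The Study Design section sets up two separate randomisations. Patients eligible for conscious sedation go 1:1:1:1 to A (PEG-ELS, single dose), B (PEG-ELS, split), C (SP/MC, single) and D (SP/MC, split). For the others: "Patients who require general anesthesia will be randomized at a 1:1 ratio to the single", that is, to single-dose groups E (PEG-ELS) and F (SP/MC). The reason given is that the local anesthesia protocol "mandates strict enforcement of nothing per oral after midnight on the day of the procedure". The section ends: "Primary end-points of this study will be measured between the participants in the all 6groups".

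The Statistical Analysis section specifies logistic regression for satisfactory preparation and repeat procedure, and proportional odds regression for tolerability, each "with the type of bowel preparation (PEG-ELS vs. SP/MC) and type of dose (single vs. split) as the independent variables". The interaction is kept if p < 0.10. The only group count in that section is "Descriptive data will be presented for all 4 groups". The Sample Size Calculation section plans "for a total of 1000 patients (250 patients per group", and the Feasibility section repeats it. Neither gives a number for E and F. Type of sedation is listed under Variables To Be Studied, but no section puts it in a model.

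The fluid rules in the Patient Education section also differ. For single-dose groups A and C: "They may continue to drink additional clear liquids until 2 hours before their colonoscopy". For E and F: "They may continue to drink additional clear liquids until midnight and then nothing to eat or drink until after their colonoscopy".

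**The concern.** Superiority of split over single dosing is a stated hypothesis, tested on the primary endpoint. The plan allows two analyses of it and does not choose.

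- **All six groups.** Split (B+D) is compared with single (A+C+E+F). General-anesthesia patients can appear only on the single-dose side, and they follow a different fluid rule. Randomisation protects the comparison of A and C with B and D, but not the part that E and F add. If general-anesthesia patients prepare worse, split dosing looks better than it is; if they prepare better, a true benefit is partly hidden.
- **A to D only.** Dose is fully randomised, but E and F have no stated analysis, against the Study Design statement.

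The mention of four groups does not settle the matter. It concerns descriptive data, and it could also mean the four preparation-by-dose cells with E pooled into A and F into C, which is the confounded case. Left open, the choice could be made after the data are seen.

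**Working it through.** **1. The plan's own figure.** For 50% versus 60%, two-sided 0.05, power 85%, the number per arm is [1.960 × √(2 × 0.55 × 0.45) + 1.036 × √(0.25 + 0.24)]² / 0.10² = 442.9, so 443, or 886 in total. This agrees with the plan. It sizes SP/MC against PEG-ELS; the documents contain no calculation for dose. The 1000 is 4 × 250, which leaves nothing for E and F.

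**2. Imbalance if six groups enter.** Let g be the general-anesthesia share of all patients. The documents do not give it, so I take 10%, 20%, 30% and 50%. The split arm is a fraction (1 − g)/2 of the trial and contains no general-anesthesia patients. The single arm is (1 − g)/2 + g = (1 + g)/2, of which g are general-anesthesia patients. Their share of the single arm is 2g/(1 + g): 18%, 33%, 46% and 67%.

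**3. Bias.** With no true dose effect, the apparent benefit of split dosing is 2g/(1 + g) × (conscious-sedation rate − general-anesthesia rate). For a 10-point gap this is 1.8, 3.3, 4.6 and 6.7 points. The sign reverses if general-anesthesia patients do better.

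**4. One case by hand.** Take g = 30%, 1000 patients over six groups, and 50% satisfactory under conscious sedation (the plan's control rate) against 40% under general anesthesia. A to D have 175 each, E and F 150 each. Split: 350 patients at 50%. Single: 650 patients at 0.50 − 0.4615 × 0.10 = 45.4%. The difference is 0.0462 with standard error √(0.25/350 + 0.454 × 0.546/650) = 0.0331, so the expected z is 1.39. The chance of exceeding 1.96 in absolute value is about 29%, against a nominal 5%.

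**5. False positives for dose, all cases.** Expected-count logistic regression with the plan's two main effects, two-sided Wald test at 0.05, no true dose effect. Simulation (20,000 trials per case) agreed within about one point.

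| Layout | Gap | g = 10% | 20% | 30% | 50% |
|---|---|---|---|---|---|
| 1000 over six groups | 5 points | 6% | 8% | 11% | 15% |
| 1000 over six groups | 10 points | 9% | 18% | 29% | 45% |
| E and F added to 1000 in A to D | 5 points | 6% | 9% | 13% | 25% |
| E and F added to 1000 in A to D | 10 points | 9% | 21% | 38% | 74% |

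With no gap the rate is 5% throughout; with a 2-point gap it is 5% to 7% in the first layout and 5% to 8% in the second. In A to D alone, or with a stratum term in the six-group model, it is 5% in every case.

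**6. Masking.** Take 1000 over six groups, a true 10-point dose benefit, and general-anesthesia patients 5 points better than single-dose conscious-sedation patients. The estimate is 10 − 5 × 2g/(1 + g): 9.1, 8.3, 7.7 and 6.7 points. Power by the same regression is 82%, 74%, 64% and 45% pooled, against 85%, 81%, 76% and 61% in A to D.

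**7. Other terms.** Preparation is allocated evenly in both strata, so its odds ratio stays at 1.50 to 1.52 when the true value is 1.50. The interaction test keeps its 10% rate if the preparation effect is the same in both strata. If that effect is 10 points under conscious sedation and 0 or 20 under general anesthesia, a false interaction enters in about 11%, 15%, 18% and 25% of trials with 1000 patients over six groups.

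**The case against.** The A to D reading has support. The sentence about six groups closes a paragraph on where procedures are done and who is blinded, and it names no model population. The trial is sized as four groups of 250 in two sections. On that reading the dose contrast is unbiased and only the missing analysis of E and F remains. This stands as a possible reading, but no section restricts the model to A to D, and it contradicts the only sentence that says which groups the primary endpoint covers.

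The size is also assumed. Neither g nor the gap is documented, a 2-point gap does little harm, and in the first layout a false-positive rate above 15% needs both a gap wider than 5 points and a sizeable g (18% at a 10-point gap and g = 20%). The second layout exceeds the stated total: 1000/(1 − g) is 1111, 1250, 1429 and 2000 patients. The Feasibility section reports 1145 inpatient colonoscopies in a year and plans 12 months of recruitment. I therefore rest the conclusion on the first layout.

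Finally, the comparison that sizes the trial is not affected, and a stratum term would remove the bias in the dose main effect as well as restriction to A to D does. Both points are right. Neither answers the concern, because dose is a stated hypothesis and the plan contains neither remedy.

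**Conclusion.** The concern holds. The model population is not specified, the text on the primary endpoint points to all six groups, and the model as written has no stratum term. Followed literally, the plan compares split with single dosing in arms that differ by rule in sedation stratum and fluid restriction. The confounding is partial, because dose is randomised within A to D. It vanishes if stratum is unrelated to cleansing.

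The direction cannot be told from the documents. Under the first layout, the dose test is nearly valid for small gaps but can reach several times its nominal error rate for a 10-point gap. With a 5-point gap in the other direction it can lose up to 16 points of power (61% − 45%). This should be settled before any analysis.

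**What to change.** 1. Estimate and test split versus single, and its interaction with preparation, in A to D only. A stratum term in the six-group model would suffice for the dose main effect, but it does not protect the interaction if the preparation effect differs between strata.
2. Compare SP/MC with PEG-ELS in all six groups, with a term for stratum as randomised (A to D versus E and F). Take it from the allocation, not from the sedation recorded at the procedure.
3. Describe six groups by stratum instead of four, and state whether the 1000 patients include E and F and how many are planned there.

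The cost is wording in the analysis and sample-size sections; no new data are needed. Precision for dose falls if 1000 is the six-group total. For 60% versus 50% with n = 500(1 − g) per arm, the normal approximation gives power Φ{[0.10√n − 1.960 × √(2 × 0.55 × 0.45)] / √(0.25 + 0.24)} = 86%, 81%, 76% and 61% at g = 10%, 20%, 30% and 50%, against 89% with all 1000 in A to D. Pooling would give 89%, 88%, 85% and 78% by simulation, but only if there were no gap between strata. The plan should state this loss.

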#### **VARIABLES TO BE STUDIED:**

- Basic demographics: Age, sex, ethnicity, income status, BMI, educational level.
- Pertinent medical history: Comorbidities including history of diabetes, stroke, Parkinson’s disease, hypertension, thyroid disease, constipation, ASA class, opiate use, TCA use, history of IBD, poor preparation in previous colonoscopies (yes/no), Charleston comorbidity index, use of anti-emetics for the bowel cleansing (yes/no).

- Procedure details: Date, indication, bowel preparation quality (reported as BPPS), type of sedation, start time of the procedure, the end time of the procedure, cecal intubation (yes/no), cecal intubation time and withdrawal time.

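### The primary logistic model adjusts for no baseline covariate although plausible predictors of cleansing are already collected; prespecifying a short list would add about 0 to 4 points of power at N=1000

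*Combined protocol and SAP*

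**What the plan says.** Statistical Analysis states that "logistic regression will be used to model satisfactory bowel preparation and need of repeat procedure". Each model is built "with the type of bowel preparation (PEG-ELS vs. SP/MC) and type of dose (single vs. split) as the independent variables"; the agent-by-dose interaction is kept if its p-value is below 0.10. No section names a covariate for adjustment.

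Variables to be Studied lists what will be recorded. Besides demographics, diabetes, stroke and Parkinson's disease, it includes "constipation, ASA class, opiate use, TCA use, history of IBD, poor preparation in previous colonoscopies (yes/no"). The same medical-history item also contains "use of anti-emetics for the bowel cleansing (yes/no"). The section does not say how any of these will be used.

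Study Design randomises in two separate streams: "Patients eligible for conscious sedation will be randomized at a 1:1:1:1 ratio" to Groups A to D, and "Patients who require general anesthesia will be randomized at a 1:1 ratio to the single"-dose groups E and F. Sedation type is recorded among the procedure details but is not in the model.

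**The concern.** In a randomised trial with a binary endpoint, adjusting for baseline variables that predict the outcome usually raises the power of the treatment test and accounts for chance imbalance in those variables. Here the candidates are already on the case report form and the model leaves them out. What is at stake is some power that would cost no extra patients.

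There is also a smaller, preventive reason. The list of variables has no stated purpose and mixes characteristics fixed before allocation with at least one that can follow it. Anti-emetics taken for the cleansing may be a response to the preparation: the protocol names nausea among the commonest reactions to PEG-ELS and records nausea in the patient survey. If covariates were ever chosen after the data were seen, such a variable could absorb part of the agent effect. A list named in advance removes that possibility.

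**Working it through.** **Inputs from the documents.** Sample Size Calculation: control rate ("we will assume that the rates of adequate bowel preparation will be 50" per cent), an increase of 10 points, 95% confidence, 85% power, 886 subjects, raised to 1000. Allocation is 1:1 between agents in both streams. I take 1000 patients as 500 per agent with the dose groups pooled.

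**Step 1: reproduce the plan's figure.** Two-sided pooled test of two proportions, mean rate 0.55:

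n per agent = [1.960·√(2·0.55·0.45) + 1.036·√(0.50·0.50 + 0.60·0.40)]² / 0.10²
= [1.960·0.7036 + 1.036·0.7000]² / 0.01
= (1.3790 + 0.7255)² / 0.01 = 442.9, so 443 per agent and 886 in total.

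This matches exactly, so the plan's figure is an unadjusted comparison of agents.

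**Step 2: unadjusted power at the planned size.** With 500 per agent:

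power = Φ[(0.10·√500 − 1.3790) / 0.7000] = Φ(1.224) = 0.890.

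**Step 3: approximate gain from adjustment.** If covariates explain a fraction R² of the outcome variance, the variance of the risk difference is multiplied by about (1 − R²), equivalent to 500/(1 − R²) patients per agent. R² is assumed, since the documents give nothing. Example at R² = 0.10: 500/0.90 = 555.6 and Φ[(0.10·√555.6 − 1.3790)/0.7000] = Φ(1.397) = 0.919. The 95% half-width is 1.96·√(0.49/500·(1 − R²)).

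| Assumed R² | Power, N=1000 | N for 85% power, 886·(1 − R²) | 95% half-width of risk difference |
|---|---|---|---|
| 0 | 89.0% | 886 | 0.0614 |
| 0.02 | 89.6% | 868 | 0.0607 |
| 0.05 | 90.5% | 842 | 0.0598 |
| 0.10 | 91.9% | 797 | 0.0582 |
| 0.15 | 93.3% | 753 | 0.0566 |

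**Step 4: simulation with the planned model.** 4,000 trials per setting, N=1000, marginal rates 50% and 60%, a logistic outcome with one normal prognostic score, and a Wald test of agent with dose in the model, without and with the score. Simulation error is √(0.9·0.1/4000), about 0.5 point per figure.

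| Assumed c-statistic | R² | Power unadjusted → adjusted | SE of log odds ratio | Conditional odds ratio | Fall in variance of standardised risk difference |
|---|---|---|---|---|---|
| 0.58 | 0.02 | 90.0% → 90.0% | 0.128 → 0.130 | 1.51 | 2% |
| 0.63 | 0.06 | 89.3% → 90.9% | 0.128 → 0.132 | 1.54 | 7% |
| 0.69 | 0.11 | 89.4% → 92.0% | 0.128 → 0.136 | 1.58 | 11% |
| 0.74 | 0.17 | 89.1% → 93.2% | 0.128 → 0.141 | 1.63 | 16% |

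The marginal odds ratio is (0.60/0.40)/(0.50/0.50) = 1.50 throughout. The standard error of the log odds ratio rises with adjustment. Power does not fall, because the conditional effect lies further from 1. The interval that narrows is the one for the standardised risk difference.

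**Step 5: sedation type.** General-anaesthesia patients receive single dosing only, so sedation type and dose are associated by design. Agent is allocated 1:1 in both streams, so omitting sedation type does not bias the agent comparison. The dose comparison lacks that protection, which is a reason to put sedation type in the model whatever is decided about the other covariates.

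**The case against.** The strongest reply is that nothing here is wrong. An unadjusted comparison of randomised groups is valid, the sample size reproduces, and 1000 patients already exceed the stated 85% power for the agent comparison. That stands, and it makes this an improvement rather than a correction.

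The benefit may also be small. As an illustration, five binary covariates with assumed prevalences of 10% to 40% and odds ratios of 1.5 each give a joint c-statistic of only about 0.60; odds ratios of 3, 2, 2, 1.5 and 1.5 give about 0.65. On that view a short, mostly binary list belongs in the lower half of the range, where the gain is nil to about 1.6 points. The simulation is also favourable: one score, complete, correctly specified and costing one degree of freedom. A real list has several coefficients to estimate and some missing history. Both points stand as limits on the size of the gain.

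Three stronger readings are tempting, and the documents support none of them.
- A reader might infer that strong predictors are being ignored. No odds ratio, c-statistic or prevalence is given for any listed variable; plausible is as far as one can go.
- A reader might infer that adjustment sharpens the planned estimate at no price. The planned estimate is an odds ratio; adjusting it changes what it estimates and raises its standard error.
- A reader might infer that the plan adjusts, or means to adjust, for anti-emetic use. Statistical Analysis names two regressors and their interaction, and the variable list is not presented as an adjustment set. The exclusion proposed here is a precaution.

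**Conclusion.** The point holds as an efficiency and prespecification improvement. The primary model uses agent and dose only, plausible pre-randomisation predictors are already collected, and naming a few of them in advance would raise power for the agent comparison at N=1000 from about 89% by about 0 to 4 points. That range rests on an assumed joint c-statistic of 0.58 to 0.74, true rates of 50% and 60%, and 500 patients per agent. With weak predictors the gain is close to nil; adjustment did not lower power in any of the four settings. The trial is not underpowered for agent on its own assumptions, and its unadjusted agent comparison would not be invalid. The change is worth making because it costs almost nothing.

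**What to change.** Before any outcome data are examined, amend Statistical Analysis to state that:

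1. The primary logistic model contains agent, dose, sedation type (which defines the two groups within which patients are randomised) and a fixed list of pre-randomisation covariates: previous poor preparation (yes / no / no previous colonoscopy), constipation, opiate use, diabetes, ASA class and age.
2. No variable that can follow allocation is used for adjustment; anti-emetic use for the cleansing is excluded by name.
3. The standardised (marginal) difference in proportions from this model is reported beside the conditional odds ratio, so that the result is on the 10-point scale of the sample size calculation.
4. The unadjusted model is kept as a sensitivity analysis.

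The cost is a few lines of text and slightly more programming, with no new data and no more patients. The downside is that the reported odds ratio becomes conditional and must be labelled as such.
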